12.3 REFERENCE SAFETY INFORMATION (RSI)

Reference Safety Information (RSI) is the information used for assessing whether an adverse reaction is expected.

The IB for Broncho-Vaxom is being used in this study, the IB will be updated annually (and/or as required) by OM Pharma.

12.4 Notification and recording of Adverse Events (AEs) or Reactions (ARs)

All AE and AR's are to be documented in the child's medical notes or other source data documents and the CRF by local site staff. AES will be collected monthly via the monthly questionnaire.

Once assessed, if the AE is not defined as SERIOUS, the AE is recorded in the participant's study file and the child is followed up by the research team.

12.5 NOTIFICATION OF AES OF SPECIAL INTEREST (AESIS)

There are no AEs the manufacturer or sponsor deem to be of special interest.

12.6 ADVERSE EVENTS THAT DO NOT REQUIRE REPORTING

Respiratory

- Cough
- Wheeze
- Lower respiratory tract illness (LRTI)

Baby symptoms would not be required to be reported as AEs:

- teething etc
- loss of appetite
- unsettled

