1.3.4 Dosage, Regimen and route

The safety of BV has been assessed in trials in infants and young children. Bodemer et al gave 3.5 mg BV or placebo once a day continuously for 9 months to children 6 months to 7 years of age with 67% of the BV group < 3 years of age [15]. There were 5 adverse events possibly related to BV (cough and diarrhoea) and 2 related to placebo (diarrhoea). Sly et al, gave oral BV 3.5 mg or placebo once a day for 10 days per month to infants 3 to 9 months of age over 2 separate winter seasons, and concluded that BV was safe and tolerable with no difference in adverse events between the groups [14]. Using a different bacteria lysate (Pro-Symbioflor), Lau et al, gave newborns 10 drops of lysate 3 times a day continuously for 7 months [28]. There were 73 adverse events reported in the active and 74 events in the placebo groups, none considered to be related to the study medication. The ongoing ORBEX study (described above) has not found safety concerns with 3.5 mg BV given once a day for 10 days per month to infants 5 to 17 months of age.

This trial is categorised as:

Type B = Somewhat higher than the risk of standard medical care, (studies are those testing authorised medicinal products according to treatment regimens outside the marketing authorization).

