12.1 GENERAL DEFINITIONS

Term	Definition
Adverse Event (AE)	Any untoward medical occurrence in a participant to whom a medicinal product has been administered, including occurrences which are not necessarily caused by or related to that product. (See section 12.6 for AEs which do not require reporting).
Adverse Reaction (AR)	An untoward and unintended response in a participant to an investigational medicinal product which is related to any dose administered to that participant. The phrase "response to an investigational medicinal product" means that a causal relationship between a study medication and an AE is at least a reasonable possibility, i.e. the relationship cannot be ruled out. All cases judged by either the reporting medically qualified professional or the sponsor as having a reasonable suspected causal relationship to the study medication qualify as adverse reactions.
Serious Adverse Event (SAE)	A serious adverse event is any untoward medical occurrence that: Results in death. Is life-threatening. Requires inpatient hospitalisation or prolongation of existing hospitalisation. Results in persistent or significant disability/incapacity. Consists of a congenital anomaly or birth defect. Other 'important medical events' may also be considered serious if they jeopardise the participant or require an intervention to prevent one of the above consequences. NOTE: The term "life-threatening" in the definition of "serious" refers to an event in which the participant was at risk of death at the time of the event; it does not refer to an event which hypothetically might have caused death if it were more severe.
Serious Adverse Reaction (SAR)	An adverse event that is both serious and, in the opinion of the reporting Investigator or medical assessor, believed with reasonable probability to be due to one of the study treatments, based on the information provided.
Suspected Unexpected Serious Adverse Reaction (SUSAR)	A serious adverse reaction, the nature and severity of which is not consistent with the information about the medicinal product in question set out in the Reference Safety Information (RSI): In the case of a product with a marketing authorisation, in the summary of product characteristics (SmPC) for that product. In the case of any other investigational medicinal product, in the investigator's brochure (IB) relating to the study in question.

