12.2 SITE INVESTIGATOR ASSESSMENT

The Principal Investigator is responsible for the care of the participant, or in their absence an authorised medic within the research team is responsible for assessment of any event for:

• **Seriousness**: Assessing whether the event is serious according to the definitions given in section 12.1.

- **Causality**: Assessing the causality of all serious adverse events/reactions in relation to the study treatment according to the definition given. If the SAE is assessed as having a reasonable causal relationship, then it is defined as a SAR.
- **Expectedness:** Assessing the expectedness of all SARs according to the definition given. If the SAR is unexpected (as per the RSI), then it is a SUSAR.
- **Severity:** Assessing the severity of the event according to the following terms and assessments. The intensity of an event should not be confused with the term "serious" which is a regulatory definition based on participant/event endpoint criteria.
 - o Mild: Some discomfort noted but without disruption of daily life
 - Moderate: Discomfort enough to affect/reduce normal activity
 - o Severe: Complete inability to perform daily activities and lead a normal life

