12.7 Adverse Events that are not unexpected

Adverse event that are not unexpected still require reporting.

Gastrointestinal

- Diarrhoea
- Abdominal pain
- Nausea and vomiting

Skin and Subcutaneous tissue disorders

- Rash (non-itchy rashes)
- Urticaria

12.8 NOTIFICATION AND REPORTING OF SERIOUS ADVERSE EVENTS (SAEs) AND SUSPECTED UNEXPECTED SERIOUS ADVERSE REACTIONS (SUSARS)

All Serious Adverse Event (SAEs) and Suspected Unexpected Serious Adverse Reactions (SUSARs) will be recorded in the child's notes, the CRF, the sponsor SAE form and reported to the sponsor (administered by the Joint Research Management Office or agreed representative) and the IMP provider (OM Pharma) as per IMP supply agreement within 24 hours of the site becoming aware of the event (except those specified in this protocol as not requiring reporting). Parents or guardians will be instructed to notify the local research team if there is any illness or hospitalisations during the study by telephone, text or email.

Nominated co-investigators (as listed) will be authorised to sign the SAE forms in the absence of the PI at the participating sites.

Suspected Unexpected Serious Adverse Reactions (SUSARs) that occur during the study will be reported to the Sponsor (JRMO or agreed representative) and IMP provider (as per IMP supply agreement) within 24 hours of the PI or co-investigator becoming aware of the event.

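### Section 12.6 exempts cough from adverse-event reporting with no exception when the study drug is suspected, so a suspected non-serious cough reaction need not be reported and sites may differ in whether they record it

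*Protocol*

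**What the plan says.** - **The exemption.** Protocol 12.6, under the title "ADVERSE EVENTS THAT DO NOT REQUIRE REPORTING", names cough, wheeze and lower respiratory tract illness, then common baby symptoms. It does not qualify the list by suspected cause.
- **Its link to the definitions.** In 12.1 the adverse event row carries the pointer "See section 12.6 for AEs which do not require reporting". The adverse reaction row has no such pointer. It counts an event as a reaction when there is a reasonable possibility of a causal link, glossed as meaning that "the relationship cannot be ruled out".
- **The recording rule.** 12.4 states: "All AE and AR's are to be documented in the child's medical notes or other source data documents and the CRF by local site staff". It mentions no exemption.
- **Causality.** The investigator's task in 12.2 is worded as "Assessing the causality of all serious adverse events/reactions in relation to the study treatment according to the definition given". There is no matching instruction for non-serious events.
- **The contrast with diarrhoea.** 12.7 lists diarrhoea among the anticipated events and says: "Adverse event that are not unexpected still require reporting".
- **The cited safety evidence.** On one study of 3.5 mg BV given daily for 9 months, 1.3.4 says: "There were 5 adverse events possibly related to BV (cough and diarrhoea) and 2 related to placebo (diarrhoea".
- **The use of the data.** Safety and tolerability is a secondary objective (2.3). Its endpoint is the count of AEs, SAEs and SUSARs (2.5.2). 14.10 tabulates events by arm and by relationship to IMP.

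**The concern.** A list of events that need no reporting is normal where the background rate is high, and cough after bronchiolitis is a fair candidate. The difficulty is that the list does not say what happens when someone thinks the drug is responsible. Cough is not an arbitrary example: in the study cited in 1.3.4 it is one of the two event types possibly related to BV, and it is mentioned only on the BV side. The other type, diarrhoea, must be reported in this trial. The protocol gives no reason for treating the two differently.

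At stake is how complete the by-relationship part of the tolerability summary is. If some sites apply 12.6 and others 12.4, the count of suspected cough reactions will partly reflect site practice.

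**Working it through.** There is no stated figure to reproduce. The check is to follow one event through the protocol: a non-serious cough that the site clinician suspects is due to the study drug.

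1. **Is it an AE that must be reported?** The AE row of 12.1 sends the reader to 12.6, which lists cough without exception. Answer: it need not be reported.
2. **Is it an AR that must be recorded?** The AR row of 12.1 has no link to 12.6, and 12.4 puts all AEs and ARs in the notes or other source documents and the CRF. Answer: it should be recorded.
3. **Does any step oblige the site to judge relatedness?** The causality instruction in 12.2 covers serious events only. Answer: no. Reaching step 2 therefore depends on a judgement that the protocol does not require.
4. **What does the analysis expect?** 14.10 splits both SAEs and other adverse events by relationship to IMP. It presumes the judgement missing at step 3.
5. **The same path for diarrhoea.** 12.7 requires it to be reported, so the conflict between steps 1 and 2 does not arise.
6. **Does another endpoint pick the event up?** Cough appears in 2.5.1 as a sign accompanying a wheeze episode. In 2.5.2 it could contribute to unscheduled attendances for lower respiratory symptoms. The monthly contact (7.8.4) gathers medication use, attendances, wheeze episodes and adverse events. None of the wheeze or attendance items carries a view on whether the drug was the cause, and an isolated cough without attendance enters none of them.

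Steps 1 and 2 give opposite answers for the same event, and step 3 supplies nothing to decide between them. A site that omits the event and a site that records it can each cite the protocol.

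**The case against.** The best defence is that 12.4 and the AR row of 12.1, read literally, already bring a suspected cough reaction into the CRF. Section 12.8.1 also gives the chief investigator medical assessment of AEs and ARs, not only of serious events. On that view 12.6 is a cross-referenced exception for ordinary AEs and leaves reactions alone. This stands in part. A reader might infer that a suspected cough reaction is shut out of the tolerability comparison, and the protocol does not support that: the event need not be reported, but nothing forbids recording it. What the defence does not supply is a sentence saying that reactions survive the exemption, or a required causality judgement for non-serious events.

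Second, exempting background cough is deliberate and reasonable in infants just out of hospital with bronchiolitis. It applies to both arms under double blinding, and the safety analysis is descriptive. All of this stands.

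Third, the evidence on cough is thin. The 5-against-2 study used continuous dosing in children with atopic dermatitis (1.2.1) aged 6 months to 7 years. The same section cites a study of 10 days per month in infants, with no difference in adverse events between groups, and an ongoing trial of that regimen without safety concerns. A reader might assume at least one event of each type on BV, count 1 to 4 coughs among the 5, and conclude that 20% to 80% of suspected reactions would be hidden here. That only enumerates an unknown split in one small study. It cannot be carried to this trial's regimen and population, and it assumes that 12.4 captures nothing.

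Nor can cough be called one of only two suspected reaction types for the product. 12.7 lists several others as anticipated, and the reference safety information is in the investigator's brochure (12.3), which is not shown.

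**Conclusion.** The point holds as an unresolved conflict between sections. 12.6 exempts cough with no exception for suspected relatedness, 12.4 says all AEs and ARs are documented, and 12.2 requires causality only for serious events. The consequence is that a non-serious cough suspected to be drug-related need not be reported and may be captured unevenly across sites. The by-relationship summary in 14.10 would then be incomplete for an event type that the protocol's own background section links to BV.

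The size is modest and cannot be put as a number from the protocol. No hypothesis test, sample size or efficacy endpoint is affected. The conclusion assumes that sites have no further instruction, in the CRF guidance or elsewhere, settling which section takes precedence; none is shown. It is a cheap improvement worth making.

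**What to change.** Add one sentence to 12.6, for example: *An event listed here that the investigator suspects is related to study drug is still recorded as an adverse reaction in the CRF; all other occurrences remain exempt.* Then make 12.1, 12.2 and 12.4 consistent with it: refer to 12.6 in the AR row and in 12.4, and state in 12.2 that the investigator's judgement of relatedness extends to such events.

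Tying the sentence to the investigator's suspicion keeps background cough out, which a bare appeal to the wide AR definition might not. No new question to parents is needed, since 12.2 places event assessment with the investigator or an authorised medic.

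The cost is a short text change and a few extra AE entries in a population where cough is common.

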12.7 Adverse Events that are not unexpected

Adverse event that are not unexpected still require reporting.

Gastrointestinal

- Diarrhoea
- Abdominal pain
- Nausea and vomiting

Skin and Subcutaneous tissue disorders

- Rash (non-itchy rashes)
- Urticaria

12.8 NOTIFICATION AND REPORTING OF SERIOUS ADVERSE EVENTS (SAEs) AND SUSPECTED UNEXPECTED SERIOUS ADVERSE REACTIONS (SUSARS)

All Serious Adverse Event (SAEs) and Suspected Unexpected Serious Adverse Reactions (SUSARs) will be recorded in the child's notes, the CRF, the sponsor SAE form and reported to the sponsor (administered by the Joint Research Management Office or agreed representative) and the IMP provider (OM Pharma) as per IMP supply agreement within 24 hours of the site becoming aware of the event (except those specified in this protocol as not requiring reporting). Parents or guardians will be instructed to notify the local research team if there is any illness or hospitalisations during the study by telephone, text or email.

Nominated co-investigators (as listed) will be authorised to sign the SAE forms in the absence of the PI at the participating sites.

Suspected Unexpected Serious Adverse Reactions (SUSARs) that occur during the study will be reported to the Sponsor (JRMO or agreed representative) and IMP provider (as per IMP supply agreement) within 24 hours of the PI or co-investigator becoming aware of the event.

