2.5.2 Secondary endpoint(s)

- 1. Impact of BV on clinical outcome measures associated with wheeze and atopy between 19-24 months:
 - Prescription for more than one salbutamol inhaler
 - · Active wheeze diagnosis on primary care record
 - Asthma diagnosis on primary care record
 - Parental report of wheeze episode time in days to first episode of wheeze from initiation of IMP or placebo.
 - · Number of unscheduled medical attendances for wheeze
 - Number of hospital admissions for wheeze
 - Number of days admitted to hospital for wheeze
 - Number of unscheduled medical attendances for any lower respiratory symptoms
 - Number of courses of systemic corticosteroids (within the 24 months post initiation of IMP or placebo)

- Number of courses of oral corticosteroids for wheeze
- Number of courses of antibiotics
- Prescription of regular oral montelukast (yes/no)
- Eczema (yes/no)
- Eczema confirmed by U.K. Working Party's Diagnostic Criteria for Atopic Dermatitis.
- 2. To assess the safety and tolerability of oral BV:
 - Number of AEs/SAEs/SUSARs across 0-24 months and 19-24 months.

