14.12 Interim analysis and criteria for the premature termination of the study

To maintain blinding all unblinded analyses for the DMC will be performed by an independent statistician who is not otherwise involved in the trial.

An interim analysis for safety will be done if requested by the DMC, the DMC will be made aware of any Suspected Unexpected Serious Adverse Reactions (SUSARs) and Severe Adverse Events (SAEs).

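### Serious cough, wheeze or lower respiratory illness events need not be reported as SAEs, and the sections that govern recording and reporting them conflict

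*Protocol*

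**What the plan says.** The AE definition in Protocol Section 12.1 carries a pointer, "See section 12.6 for AEs which do not require reporting". Section 12.6, headed "ADVERSE EVENTS THAT DO NOT REQUIRE REPORTING", lists three respiratory terms: cough, wheeze and "Lower respiratory tract illness (LRTI"). It also lists minor infant symptoms such as teething. No seriousness limit is attached to any of them.

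The opening sentence of Section 12.8 requires SAEs and SUSARs to be recorded in the notes, the CRF and the SAE form, and sent to the sponsor and the IMP provider within 24 hours, "except those specified in this protocol as not requiring reporting". A later paragraph of 12.8 has no such exception: "Suspected Unexpected Serious Adverse Reactions (SUSARs) that occur during the study will be reported to the Sponsor" and to the IMP provider, again within 24 hours.

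Section 12.4 says that every AE and AR is documented in source and in the CRF. The safety endpoint in 2.5.2 is "Number of AEs/SAEs/SUSARs across 0-24 months and 19-24 months". Section 14.10 reports children with an SAE or AE by arm and by relationship to the IMP. Section 14.12 says that "the DMC will be made aware of any Suspected Unexpected Serious Adverse Reactions (SUSARs) and Severe Adverse Events (SAEs").

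**The concern.** Every child enters after a hospital admission for bronchiolitis and is treated for 24 months. Wheeze and lower respiratory illness are the conditions this population can be expected to have, and some episodes will lead to admission. An exemption for expected disease events can be reasonable. It then needs a stated limit, or a substitute route by which an imbalance between arms would be seen. Here the exemption has no seriousness limit, it reaches into the SAE rule, and no substitute is stated.

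At stake are the completeness of a secondary endpoint, the safety tables, and the SAE data given to the committee that assesses safety. Causality review is affected too: under 12.8.1 the Chief Investigator reviews seriousness, relatedness and expectedness within 72 hours of receiving an SAE, so an event that is never sent gets no such review.

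Section 1.3.4 adds a smaller point. In an earlier trial of the same product, "There were 5 adverse events possibly related to BV (cough and diarrhoea) and 2 related to placebo (diarrhoea"). One of the exempt terms has therefore already been judged possibly related. That sentence gives no separate count for cough and calls no event serious, so it carries limited weight.

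**Working it through.** No figure in the plan underlies this point, so the check is a trace through the text.

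1. **Can a listed event be serious?** Yes. Section 12.1 includes inpatient hospitalisation and death among the SAE criteria. A wheeze or LRTI episode that leads to admission qualifies.

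2. **Which list does the 12.8 exception refer to?** Section 12.6 is the only candidate. Section 12.7 says that its own events still have to be reported.

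3. **Could 12.6 be meant for non-serious events only?** The sentence in 12.8 that carries the exception governs only SAEs and SUSARs. If 12.6 held only non-serious events, the exception would remove nothing. Teething, poor appetite and being unsettled will rarely be serious, so in practice the exception works through the three respiratory terms. Nothing elsewhere restores reporting when a listed event is serious.

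4. **What depends on SAE reporting?** The counts in 2.5.2, the by-arm summary in 14.10, the Chief Investigator's review in 12.8.1 and the information to the DMC in 14.12.

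5. **Do other data fill the gap?** In part.
   - Sections 2.5.2 (months 19-24) and 2.5.3 (months 0-24) collect the number of wheeze admissions, days in hospital for wheeze, and unscheduled attendances for lower respiratory symptoms.
   - There is no admission count for LRTI without wheeze.
   - None of these outcomes carries a causality assessment.
   - No passage sends them to the DMC by arm.
   - Parents are told to notify the site of hospitalisations (12.8), but no rule turns that notice into an SAE record for an exempt term.

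6. **Are the sections consistent?** No. Section 12.4 documents all AEs in the CRF, while 12.6 exempts some. The first sentence of 12.8 applies the exception to SUSARs as well as SAEs; its last paragraph applies none.

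7. **Size.** The only event rates given are the 22% and 13.2% in Section 14.1. With 894 / 2 = 447 children per arm, these give 447 × 0.22 = 98 and 447 × 0.132 = 59 children with confirmed wheeze in months 19-24. That shows how common an exempt event is expected to be. It says nothing about how many episodes are serious, and no rate of respiratory admission or death is stated.

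**The case against.** The strongest reply is that the exception follows directly after the 24-hour notification clause and speaks of reporting. It may therefore waive expedited notification only and leave recording untouched. Section 12.4 supports this, and 12.2 asks the investigator to assess any event for seriousness and all serious events for causality. If serious listed events are on the CRF, they can be counted under 2.5.2 and 14.10. This stands as a possible reading, and it is why the point is that events can be left out. But 12.8 does not say so, and the same sentence also governs entry in the CRF and on the SAE form.

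Second, an event judged related and unexpected has a route to the sponsor through the last paragraph of 12.8, and the DMC is told of SUSARs. That also stands, but it does not cover serious events judged unrelated, which matter for a comparison between arms.

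Third, the DMC is unblinded (7.5), meets regularly to assess safety data under a charter not shown here (23.3), and may request a safety interim analysis (14.12). A reader might infer that it is told only of SUSARs and SAEs. Section 14.12 does not say that, and nothing bars the DMC from asking for respiratory admissions by arm. What is missing is a stated provision.

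**Conclusion.** The point holds as a defect of drafting with consequences for safety monitoring. As written, a serious cough, wheeze or LRTI event need not be reported as an SAE and can be absent from the safety endpoint, the safety analysis and the SAE data reaching the DMC. The conclusion rests on reading the 12.8 exception as referring to 12.6, which is the only list that fits.

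Three stronger readings go too far:
- **All respiratory admissions and deaths are missing.** Only three terms are listed. Deaths are not named in 12.6; they would be affected only by inference, and only when classed under one of those terms. Wheeze admissions are in the trial data as outcomes, and 2.5.2 does not label its admission counts as parent-reported; that label belongs to the exploratory set in 2.5.3.
- **A number of lost events.** An assumed 5-15% admission rate would give 39 to 116 of the 774 children in the UK target (0.05 × 774; 0.15 × 774), or 45 to 134 of the combined 894. No document supports that rate, and the point does not need it.
- **A different class of events goes to the DMC because 14.12 says Severe.** The abbreviation SAE is defined as serious in 12.1, so this is a wording slip.

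**What to change.** Choose one of two routes in Section 12.6:
- limit the exemption to non-serious events, so that any listed event meeting a 12.1 criterion is handled as an SAE; or
- keep the waiver of expedited reporting for expected respiratory admissions, but state that serious listed events are still recorded on the eCRF with seriousness and causality, counted in 2.5.2 and 14.10, and tabulated by arm for the DMC.

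In either case, state in 12.8 that the exemption never applies to SUSARs, and reconcile 12.4, 12.6, 12.8, 14.10 and 14.12 so that recording, notification and counting follow one rule. As an editorial correction, the word Severe in 14.12 should read Serious.

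The cost is a protocol amendment and some additional forms for sites. The second route keeps the expedited workload as it is now.
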